4. SELECTION, WITHDRAWAL, AND REPLACEMENT OF PATIENTS

4.1 Study Population

This study aims to enroll 40 eyes from patients with both cataract and glaucoma.

4.1.1 Inclusion Criteria

A patient must meet the following criteria to be eligible for inclusion in the study:

- At or over the age of 21
- Cataract surgery candidate and glaucoma present in at least one eye
- Minimally-invasive glaucoma surgery candidate in at least one eye. Defined by having ocular hypertension requiring a medication, OR as by having mild, moderate, or severe glaucoma that is sufficiently stable and appropriate for operation.

4.1.2 Exclusion Criteria

A patient who meets any of the following criteria will be excluded from the study:

- Maintains regular use (daily or more) of systemic or ocular steroids at time of enrollment
- Maintains regular use (daily or more) of systemic or ocular nonsteroidal anti-inflammatory drugs at time of enrollment
- Anterior chamber cells present at time of enrollment
- Recent febrile illness that precludes or delays participation for 3 months
- Pregnancy or lactation
- Known allergy to dexamethasone
- Known allergy to prednisolone
- Treatment with another investigational drug within the last 20 years
- Current recreational drug use
- Preexisting ocular pathology likely to confound the visual acuity or comfort endpoints including but not limited to: severe corneal scarring, ocular surface disease, diabetic retinopathy, or macular edema
- Corneal or retinal procedures (laser or incisional) during the study period and 6 months prior in either eye

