4.2 Treatment Logistics and Accountability

4.2.1 Packaging, Labeling, and Storage

Intracanalicular dexamethasone insert must be stored in a secure area accessible only to the Investigator and their designee(s) and refrigerated and stored between 2° C and 8° C. Intracanalicular dexamethasone insert contains 0.4 mg dexamethasone and is designed to provide a sustained and tapered release of therapeutic levels of dexamethasone to the ocular surface for up to 30 days for the reduction of post-surgical inflammation and pain associated with ocular surgery. Dexamethasone is an anti-inflammatory 9-fluoro-glucocorticoid (also termed a glucocorticoid agonist) and is the active ingredient found in MAXIDEX® 0.1% (dexamethasone ophthalmic suspension), which contains approximately 50 µg of dexamethasone per drop.

Study inserts will be supplied by Ocular Therapeutix in a sealed foil pouch containing one intracanalicular dexamethasone insert in a foam carrier.

Study inserts will be shipped to the site via overnight shipping using cold packs to maintain a temperature of 2° to 8° C. The Investigator, or an approved representative (e.g. pharmacist), will ensure that all study drug inserts are stored in a secured area, under recommended storage conditions and in accordance with applicable regulatory requirements. The shipping box is to be opened and stored immediately at the site in a refrigerator intended

for investigational products at a temperature of 2° to 8°C.

When the insert is removed from the refrigerator, it should be visually inspected. Exposure of the insert to temperatures outside these limits it not recommended. Records of actual storage conditions (i.e. temperature log) at the study site must be maintained; and must include a record of the dates, when the refrigerator was checked, the initials of person checking, and the temperature.

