6. RISK/BENENFIT ASSESSMENT

6.1 Risks

Use of corticosteroids on the eye, whether they are steroid drops or sustained-release inserts like DEXTENZA®, can worsen glaucoma with damage to the optic nerve by increasing intraocular pressure. Corticosteroids may suppress the host immune system and increase risk for bacterial infection, fungal infection, and viral infection. The use of steroids after eye surgery may delay healing and increase the incidence of bleb formation. DEXTENZA® may be ineffective. DEXTENZA® may cause discomfort in the eye. DEXTENZA® may involve unforeseeable risks. DEXTENZA® may involve additional risks that are currently unknown. Because DEXTENZA® is FDA approved for the treatment of postoperative ocular inflammation and pain, minimal overall risk to patients is anticipated.

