6.4 Alternative Treatments

Steroid eye drops are the standard-of-care alternative to DEXTENZA®. Also, DEXYCU® is another type of sustained-release dexamethasone drug that is currently FDA-approved for the same indication as DEXTENZA®. DEXYCU® is injected inside the eye, behind the iris of the eye. No currently published study has compared DEXTENZA® to DEXYCU®, so the relative advantages and disadvantages are not clearly known.

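### The steroid exclusion has no look-back, so residual steroid can raise the baseline IOP from which a primary endpoint is measured

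*Combined protocol and SAP*

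**What the plan says.** Section 4.1.2 excludes a patient who "Maintains regular use (daily or more) of systemic or ocular steroids at time of enrollment". No other exclusion concerns earlier steroid treatment, apart from allergy to the two study steroids. Section 4.3 lets patients continue medication for other conditions at their physician's discretion and sets no limit on steroids.

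Section 4.2.1 describes the study insert as giving "sustained and tapered release of therapeutic levels of dexamethasone to the ocular surface for up to 30 days". Section 6.1 says that steroids on the eye, as drops or inserts, "can worsen glaucoma with damage to the optic nerve by increasing intraocular pressure". Section 6.4 names a second sustained-release dexamethasone product, injected inside the eye.

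The first primary endpoint in section 8.2 is the mean Goldmann IOP reduction at 1 and 3 months, with a comparison between groups. The baseline visit may fall anywhere from Day -90 to Day -1 (section 5.2.1). Section 9 promises hypothesis testing without naming a model or a baseline adjustment.

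Two other exclusions do carry dates. One covers "Corneal or retinal procedures (laser or incisional) during the study period and 6 months prior in either eye". The other is "Treatment with another investigational drug within the last 20 years".

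**The concern.** A rule based on daily use at one moment fits drops and tablets that are being taken now. It does not fit an exposure that outlasts the last dose or needs no daily dose, and the study product is itself of the second kind. On the wording, steroid drops stopped the day before enrollment, an injection two weeks earlier and a single sustained-release placement all pass the criterion.

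What is at stake is the baseline of a primary endpoint. If a recent steroid has raised the baseline Goldmann reading and the effect has gone by follow-up, the fall is counted as IOP reduction although neither the surgery nor the study treatment produced it. With 20 eyes per arm, a few such eyes can move an arm's mean, and chance may place more of them in one arm than in the other.

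**Working it through.** **Does another provision close the gap?** Each candidate gives partial cover at most.

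- The pathology exclusion is for "Preexisting ocular pathology likely to confound the visual acuity or comfort endpoints". It removes macular edema and diabetic retinopathy, which are possible reasons for a steroid depot, but it does not name IOP.
- The 6-month look-back covers laser or incisional corneal and retinal procedures. It does not mention steroid injections or inserts.
- Anterior chamber cells at enrollment exclude a patient, but a residual steroid may suppress those cells.
- Section 4.1.1 requires glaucoma stable enough for surgery. That is a judgement with no reference to steroid history.
- Screening collects medical history and concomitant medications (section 5.1, Table 1), but no rule says what to do with a recent steroid found there.

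**Which visit is affected?** Every eye receives steroid again after surgery. The insert releases for up to 30 days, so in that arm the 1-month reading comes at or near the end of renewed exposure, and a wash-out fall need not show. By 3 months the insert is spent. The documents do not state how long the prednisolone course lasts. The argument therefore bears mainly on the 3-month reading.

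**Size.** The plan gives no exposure frequency, steroid response, IOP standard deviation or power calculation, so there is no figure to reproduce. What follows is illustration.

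From the plan: 40 eyes, 20 per arm. Assumed: k exposed eyes, each with baseline IOP raised by e = 3 to 8 mmHg, fully resolved by the endpoint visit.

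Overstatement of the mean reduction, averaged over both arms = k × e / 40:

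- k = 2: 2 × 3 / 40 = 0.15 to 2 × 8 / 40 = 0.40 mmHg
- k = 4: 4 × 3 / 40 = 0.30 to 4 × 8 / 40 = 0.80 mmHg
- k = 8: 8 × 3 / 40 = 0.60 to 8 × 8 / 40 = 1.60 mmHg

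**Effect on the comparison.** Shift in the between-arm difference = (x₁ − x₂) × e / 20, where x₁ and x₂ are the exposed eyes in each arm. Exposure precedes randomization, so x₁ − x₂ has expectation zero. Treating allocation as a random 20/20 split of 40 independent eyes:

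- k = 2: chance that both fall in one arm = 2 × C(20,2) / C(40,2) = 380 / 780 = 0.49
- k = 4: chance of an even split = C(20,2)² / C(40,4) = 36,100 / 91,390 = 0.395, so the chance of an imbalance of at least 2 eyes is about 0.60
- A 2-eye imbalance shifts the difference by 2 × 3 / 20 = 0.3 to 2 × 8 / 20 = 0.8 mmHg

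This ignores stratification by MIGS type and the few two-eye patients. In those patients one eye goes to each group (section 3.1), so a systemic exposure would balance.

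**Scale.** With an assumed SD of 3, 4 or 5 mmHg for IOP change, two-sided alpha 0.05 and 80% power, the detectable difference is SD × √(2/20) × (1.960 + 0.842) = 2.7, 3.5 or 4.4 mmHg.

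**The case against.** The strongest reply is that the exposure is rare and largely closed off already. The sustained-release products the protocol names are for use after eye surgery, and the study eye has not yet had its cataract operation. Many eyes given a steroid depot would fail on macular edema, diabetic retinopathy, anterior chamber cells or the 6-month procedure rule. This narrows the gap mainly to recently stopped drops and some injections. It does not close it, because none of those provisions is a steroid look-back.

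A second reply is that randomization protects the comparison. In expectation it does. A reader might infer that the treatment comparison of IOP is biased; the documents do not support that. What remains is the within-group reduction, which section 8.2 lists alongside the comparison, plus noise and chance imbalance.

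A reader might also infer larger effects. Three exposed eyes in one arm, each raised by 10 mmHg, would inflate that arm's reduction by 3 × 10 / 20 = 1.5 mmHg. Both inputs are assumptions with no basis in the documents. Even with 3 exposed eyes among 40, the chance that all fall in the same arm is 2 × 1,140 / 9,880, about 23%.

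Nor do the inflammation and macular endpoints share the problem. Absence of cells at 30 days and CME at 90 days are not changes from baseline.

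**Conclusion.** The gap in the wording is real, and nothing else in the plan closes it. The consequence is modest: a possibly overstated within-group IOP reduction, mainly at 3 months, and some added noise and chance imbalance between arms. On the assumed inputs the overstatement is 0.15 to 0.8 mmHg for 2 to 4 exposed eyes of 40, well below the illustrative detectable differences. The true size cannot be determined from the documents, and it is small if exposure is rare.

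A reader might set the missing steroid look-back against the 20-year investigational-drug rule and conclude that the second is a misplaced washout that should be shortened. The documents do not support that. It is a separate, strict criterion on a different exposure. It affects who can be recruited, not the IOP baseline. No reason is given for the figure, and whether it is intended cannot be told from the text, so a request for confirmation is all that is warranted.

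**What to change.** Extend the steroid criterion in section 4.1.2 to cover any ocular steroid in the study eye (topical, periocular, intraocular or sustained-release), or systemic steroid, within a stated period before the baseline Goldmann reading and up to surgery. The second limit is needed because baseline may precede surgery by as much as 90 days. The sponsor sets the period. It should be no shorter than the 30-day release in section 4.2.1. That figure is a floor, since a release time does not show how long IOP takes to recover.

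The check can use the medical history and medications already collected at screening, with an update at surgery. The cost is one revised criterion and a few recently treated eyes deferred.

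Separately, confirm that the 20-year investigational-drug window is intended.

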1.5 Rationale for Study Design

This prospective study will enroll 40 eyes from a variable number of total patients. The total patient number may vary due to the enrollment of both eyes from some patients where possible. All eyes will receive concomitant cataract and MIGS surgery. Each eye will be randomized to receive either insertion at the end of the surgery or to a standard of care prednisolone acetate 1% eye drop regimen. All eyes will receive the standard of care topical ofloxacin antibiotic regimen. The experimental group will consist of the 20 eyes receiving DEXTENZA® insertion. The control group will consist of the 20 eyes placed on the prednisolone eye drop regimen.

In terms of study procedures, the majority are among cataract and MIGS preoperative, perioperative, and postoperative standards of care. Such procedures include: pachymeter, indirect ophthalmoscope, slit lamp exam, BCVA, IOP, visual field, OCT RNFL, corneal endothelial microscopy and gonioscopy. The ocular response analyzer will record corneal hysteresis data. Corneal hysteresis, as a measure of the cornea's ability to dampen in response to an external force, has been shown in multiple studies to serve as an independently valuable risk factor indicating glaucoma progression (Lam et al. 2010; Agarwal et al. 2012; Medeiros et al. 2013). To better inform the treatment of glaucoma patients during this study, the ocular response analyzer is a valid and useful tool.

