3. STUDY DESIGN

3.1 Study Description and Duration

This prospective, open-label, single-center, randomized, fellow-eye, October 18, 2020 Page 7

investigator-initiated clinical study seeks to investigate the safety and efficacy of the dexamethasone insert in glaucoma patients after concomitant MIGS and cataract surgery. After screening a given patient for inclusion and exclusion criteria, and gaining informed consent, the patient's eligible eye will be randomized to either receive the dexamethasone insert after concomitant cataract-MIGS or to receive prednisolone acetate 1% eye drops after concomitant cataract-MIGS. For participants who enroll only a single eye, block randomization will be performed to ensure that the type of MIGS surgeries will be balanced between the two treatment groups. This stratification is necessary because it is possible that different MIGS devices can confound endpoint measurements, such as IOP control. A stratified block randomization schedule will be developed in advance by the sub-investigator through a computer program, and each assignment will be placed in opaque, sealed envelopes that will be labeled with the stratifying MIGS category. The primary investigator will only open an envelope after a patient is enrolled and the MIGS type that is suitable for the patient is determined. In the few cases where a patient enrolls both eyes, the same MIGS surgery will be performed for each eye. Under such a circumstance, simple randomization will be sufficient to determine whether the first or second eye operated on will receive the dexamethasone insert. The other eye will be placed in the prednisolone acetate 1% eye drops group.

Per enrolled eye, the study period will last for approximately 90 days after surgery, consisting of four postop follow-up visits. At Day 1, Day 7, Day 30, and Day 90, primary and secondary endpoints will be assessed alongside standard-of-care procedures. Adjusting for enrollment period, the study will last a total of approximately twelve months.

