5.2 Study Visit Descriptions

5.2.1 Study Procedures

Screening/Baseline (Day -90 to-1)

After the patient has provided informed consent, the following information will be collected:

- 1. Inclusion/exclusion
- 2. Demographics
- 3. Medical history and concurrent illnesses
- 4. Concomitant medications
- 5. Best-corrected visual acuity as measured by ETDRS chart at 4m
- 6. Visual field mean deviation
- 7. Ophthalmic examination
- 8. Grade cataract density and identify type
- 9. Glaucoma type and severity
- 10. OCT RNFL & Macula
- 11. Goldmann Intraocular pressure and CATS intraocular pressure
- 12. Corneal endothelial specular microscopy
- 13. Gonioscopy
- 14. Ocular Response Analyzer
- 15. Pachymeter
- 16. Indirect ophthalmoscope
- 17. Type of IOL
- 18. Type of MIGS device (Hydrus, iStent, canaloplasty, or Kahook Dual-Blade)
- 19. Subject reported AEs prior to surgery

Surgical visit/Day 0

- 1. Indicate the incision type, location, and size
- 2. Type of IOL
- 3. Type of MIGS device (Hydrus, iStent, canaloplasty, or Kahook Dual-Blade)
- 4. Record any surgical complications
- 5. Intracanicular dexamethasone insert

Day 1 postop (+/- 2 days)

- 1. Concomitant medications
- 2. Best-corrected visual acuity as measured by ETDRS chart at 4m
- 3. Ophthalmic examination
- 4. Goldmann Intraocular pressure and CATS intraocular pressure
- 5. Subject reported AEs after surgery
- 6. Anterior chamber cell count
- 7. Anterior chamber cell flare
- 8. Insert Visualization
- 9. Prescribe post-operative topical therapy regimen

Day 7 postop (+/- 2 days)

1. Concomitant medications

October 18, 2020 Page 13

- 2. Best-corrected visual acuity as measured by ETDRS chart at 4m
- 3. Ophthalmic examination
- 4. Goldmann Intraocular pressure and CATS intraocular pressure
- 5. Subject reported AEs after surgery
- 6. Anterior chamber cell count
- 7. Anterior chamber cell flare
- 8. Insert Visualization

Day 30 postop (+/- 7 days)

- 1. Concomitant medications
- 2. Best-corrected visual acuity as measured by ETDRS chart at 4m
- 3. Ophthalmic examination
- 4. Goldmann Intraocular pressure and CATS intraocular pressure
- 5. Subject reported AEs after surgery
- 6. Anterior chamber cell count
- 7. Anterior chamber cell flare
- 8. Insert Visualization
- 9. Ocular Comfort Index

3 month postop (+/- 14 days)

- 1. Concomitant medications
- 2. Best-corrected visual acuity as measured by ETDRS chart at 4m
- 3. Ophthalmic examination

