8.2 Primary and Secondary Endpoints

Primary Endpoints

Effect of dexamethasone insert through Day 90 as measured by -

- 1. Mean Reduction in IOP at 1 and 3 months as measured by Goldmann Applanation Tonometer and comparison between groups
- 2. Mean change in ETDRS BCVA at 1 and 3 months and comparison between groups
- 3. Difference in adverse events between the two groups
- 4. Difference in number of glaucoma medications between the wo groups at 3 months

Secondary Endpoints

Through Day 90 as measured by -

- 1. Number of patients requiring supplemental prednisolone acetate 1% eye drops
- 2. Incidence of CME at 90 days as seen on OCT

- 3. Difference in Ocular Comfort Index between the two groups at 1 month and 3 months
- 4. Difference in percentage of patients with absence of anterior chamber cells at 30 days between groups

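### An exclusion criterion covering corneal or retinal procedures during the study period can first be met after randomisation, and no analysis set or withdrawal rule protects the eyes it would remove

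*Combined protocol and SAP*

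**What the plan says.** The exclusion list in Section 4.1.2 opens with "A patient who meets any of the following criteria will be excluded from the study". Its last entry is "Corneal or retinal procedures (laser or incisional) during the study period and 6 months prior in either eye". Three other entries (regular steroid use, regular NSAID use, anterior chamber cells) are tied explicitly to the time of enrolment. This one is not, and it does not say that the procedure must be planned.

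Section 3.1 defines the window: "Per enrolled eye, the study period will last for approximately 90 days after surgery, consisting of four postop follow-up visits". On allocation for single-eye participants it says: "The primary investigator will only open an envelope after a patient is enrolled". For two-eye participants, one eye goes to each arm.

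The primary endpoints in Section 8.2 include IOP and BCVA at 1 and 3 months, the number of glaucoma medications at 3 months, and "Difference in adverse events between the two groups". CME on OCT at 90 days is secondary.

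Section 9 is the whole statistical plan. It promises hypothesis tests and descriptive summaries and defines no analysis set. The heading of Section 4 mentions withdrawal and replacement, but no rule on either follows.

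**The concern.** Eligibility criteria should rest on facts known before allocation. This one reaches into follow-up. If a site or analyst enforces it there, an eye leaves because of something that happened after treatment. That event may be related to treatment, and in an open-label, single-centre study it is judged by people who know the arm. The two groups then compared are no longer the groups that were randomised.

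The criterion acts on the patient and refers to either eye. A procedure in one eye could therefore remove both eyes of a two-eye participant, one from each arm. In a single-eye participant, a procedure in the non-study eye could remove the study eye.

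At stake are the primary comparisons of IOP, BCVA and glaucoma medications, and adverse events that arise after the eye has left. The trial's stated rationale is to settle safety concerns about IOP, so losing eyes with a difficult course would matter.

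**Working it through.** The documents contain no figure to reproduce here: no procedure rate, power calculation or dropout allowance. The check is mainly of the text.

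**1. Can the criterion be met after randomisation?** Allocation follows enrolment, the insert is placed at surgery, and the study period is roughly the 90 days after surgery (Section 3.1). A procedure on, say, Day 20 falls inside the criterion and after allocation. So yes.

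**2. Can screening settle it?** In Section 5.2.1 the eligibility check ("1. Inclusion/exclusion") appears only in the Screening/Baseline list, Day -90 to -1, and Table 1 agrees. A check on those days can establish past and planned procedures. It cannot establish that none will occur later.

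**3. What would be kept if an eye left early?** Table 1 marks two rows under Early Termination: surgical complications and participant-reported adverse events. Section 5.2.3 also requires adverse events during the study to be recorded.

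| Data | Endpoint level | Marked at Early Termination? |
|---|---|---|
| Adverse event leading to the procedure | Primary | Yes |
| Adverse events after leaving | Primary | No later visit |
| IOP | Primary | No |
| BCVA | Primary | No |
| Glaucoma medications | Primary | No |
| OCT (CME) | Secondary | No |

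**4. Does any rule keep the eye in the analysis?** None was found in Section 4 or Section 9.

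**5. Scale.** From Section 1.5, there are 40 eyes, 20 per arm. One eye is 1/20 = 5 percentage points of an arm.

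*Illustration with assumed rates.* If a proportion p of eyes meets the criterion during follow-up and eyes are independent, the chance that at least one of 40 does is 1 − (1 − p)^40, and the expected number is 40p.

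| Assumed p | Expected eyes | Chance of at least one |
|---|---|---|
| 1% | 0.4 | 33% |
| 2% | 0.8 | 55% |
| 5% | 2.0 | 87% |
| 10% | 4.0 | 98.5% |

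*Illustration with assumed IOP.* If k of 20 eyes have IOP d mmHg above the rest of their arm, dropping them lowers the arm mean by (k/20) × d. For d = 5 to 10, k = 1 gives 0.25 to 0.5 mmHg, and k = 2 gives 0.5 to 1.0 mmHg.

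None of p, k or d comes from the documents. The tables show only that a small count matters with arms of this size.

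**The case against.** The strongest reply is that this is an ordinary eligibility screen, loosely worded. Inclusion and exclusion are checked only at Screening/Baseline, no later visit repeats the check, and nothing instructs the investigator to remove a randomised eye. On that reading the sponsor meant that no such procedure should be planned. This is plausible and it stands as a reading of intent. It does not remove the problem, because the text says something else and no other section limits it.

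Three stronger readings might be inferred, and the documents do not support them.

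- *The adverse event itself disappears from the primary safety endpoint.* The Early Termination column and Section 5.2.3 both provide for recording it, and Section 7.2 requires all serious events to be reported whatever their cause. Section 7.2 limits recording to medically relevant events, but a complication that needed a procedure would hardly be filtered out. Nothing says that recorded events are deleted from the analysis. The gap is that nothing guarantees they are counted.
- *Such procedures are mostly responses to complications of treatment.* The documents do not say so. Section 6.1 names no corneal or retinal procedure among the risks, and the rescue treatment in Section 5.3 is topical. Only the subset of complications leading to such a procedure is affected.
- *The second eye's study surgery triggers the criterion and so conflicts with two-eye enrolment.* The protocol never calls cataract or MIGS surgery a corneal or retinal procedure. Section 1.5 expressly provides for "enrollment of both eyes from some patients where possible", and Section 10.8 compensates for it. The documents also give no interval between the two surgeries.

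**Conclusion.** The concern holds in a limited form. As written, the criterion permits removal of randomised eyes on a post-treatment event in an open-label trial, and nothing in Section 4 or Section 9 offsets that. The likely loss is later follow-up: the remaining IOP, BCVA, glaucoma-medication and OCT data, and any later adverse events. The triggering event would probably be recorded.

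The direction and size of any bias are unknown. They depend on how often such procedures occur, whether they differ by arm, and whether the site applies the criterion after randomisation, and the documents settle none of these. The only firm scale is that each eye lost is one twentieth of an arm. If the site uses the criterion purely as a screen for planned procedures, no eye is lost. The ambiguity should still be closed, because an open-label study should not leave that decision to be made once the arm and the outcome are known.

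**What to change.** Reword the criterion in Section 4.1.2 to cover laser or incisional corneal or retinal procedures in either eye within 6 months before enrolment, or already planned at enrolment to take place during the study period. Optionally, add that the study's own cataract and MIGS surgery does not count.

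Add one sentence, in Section 4 or Section 9: an eye that needs such a procedure after randomisation remains in follow-up and is analysed in the arm to which it was randomised. The underlying condition is recorded as the adverse event, with the procedure recorded alongside it. The condition is what should be counted, because Section 7.1.1 defines an adverse event as an untoward occurrence, sign, symptom or disease.

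The cost is one or two sentences in a protocol amendment, with no extra visits or eyes. The downside is that a few retained eyes may have IOP or BCVA values affected by the procedure. A sensitivity analysis without the post-procedure values of those eyes would show how much that matters.
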